In PsA but also in chronic arthritis in general, integrating imaging in clinical practice is the challenge of the near future and for clinical feasibility it is essential to identify an US composite score that could explore all the domains of the disease, especially in the polymorphic PsA.

In 2012 *Gutierrez et al.* developed a Power Doppler composite score focused on joints, tendons, entheses, skin and nails and the final target was to define the overall disease activity.⁽¹³⁾ The German US7-joints score is another viable tool for examining patients with chronic arthritis in daily practice. Developed mainly for RA, it was also effective for monitoring therapy in peripheral PsA.⁽¹⁴⁾ More recently *Ficjan et al* developed two new US composite scores (PsASon-13 and PsASon-22), derived from a total ultrasound score (68 joints/14 entheses) in order to have a high sensitivity to detect PsA features and a good feasibility in clinical practice.⁽¹⁵⁾ However no simplified scores are fully validated in terms of content, construct and criterion so far. For this reason extensive US evaluations are needed to assess PsA in clinical practice and research.

AIM

The aim of this study is to identify clinical and US predictors of achieving MDA in PsA patients with active peripheral arthritis starting a new course of therapy.

Identifying prognostic factors of achieving remission or low disease activity will allow a better selection of patients with poorer outcome and a following improvement of the therapeutic strategies. Furthermore the possibility that US could be an added prognostic value makes this study a clear example of integration between the clinic and US. This study will respond to the need of tailoring treatment that would allow clinicians to practice a more effective and personalized medicine, optimizing the outcomes of patients with PsA as well as the treatments management.

STUDY OBJECTIVES

PRIMARY OBJECTIVE

In clinically diagnosed PsA with clinically active joint disease starting a new course of therapy, to evaluate the additional value of US-score (US-score PsA-SIR) over clinical examination in detecting patients achieving MDA at 6 months.

SECONDARY OBJECTIVES

In clinically diagnosed PsA with clinically active joint disease starting a new course of therapy:

- to evaluate the additional value of US over clinical examination in detecting patients:
 - achieving MDA at 12 months (including sustained)

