A total of 30 static images per US-lesion type (synovitis, enthesitis, tenosynovitis, erosion, bony apposition) with 50% of presence of lesions will be submitted to scoring through an on-line electronic platform. A reference atlas will be provided to the investigators before the exercise. A second exercise could be offered to investigators who did not achieve a minimum level of kappa after further training at one of the Centres of the PIs.

SCREENING VISIT

The aim of this visit is to identify a patient who might be suitable for inclusion in the study.

- Consent: Inform the patient about the nature and objectives of the study and obtain his/her written informed consent;
- Check inclusion/exclusion criteria;
- Check cumulatively CASPAR criteria since the onset of PsA;
- Assign patient number (PN) in sequential order, if the patient is suitable for the inclusion in the study.

BASELINE VISIT

The aim of this visit is to confirm that the patient is appropriate for inclusion in the study, determine disease activity state, undertake a complete high resolution ultrasound assessment and X-ray of hands and feet. If a X-ray has been already done within the 6 months before the study entry is not requested to perform a further scanning.

- Record in Case Report Form:
 1. demographic and life-style variables (*smoking, alcohol consumption, BMI*);
 2. drug history (*including past adverse events*);
 3. typical comorbidities associated to PsA (*obesity, diabetes, hypertension, metabolic syndrome non-alcoholic fatty liver disease, IBD, uveitis, anxiety/depression*) and other comorbidities (*e.g. neoplasms, cardiovascular disease, Charlson comorbidity index*);
 4. onset of symptoms and disease duration;
 5. define clinical subset of PsA;
 6. CPR (mg/dl), ESR;
 7. RF, ACPA and HLA B27 (if available);
 8. treatment to be started;
- Procedures for psoriatic arthritis:
 1. Swollen (68) and Tender (66) Joints Count;
 2. Enthesal assessment;
 3. Tender Dactylitis Count;

- Procedures for psoriasis:
 1. Body Surface Area (BSA);
- Questionnaires:
 1. Physician completes VAS Physician global assessment of disease activity (joint and skin) 0-100;
 2. Patients completes pain VAS (0-100), global VAS (0-100), HAQ, BASDAI, PSAID12;
- US assessment:
 1. US-score PsA-SIR;
- X-ray assessment of hands and feet:
 1. Posterior-anterior radiographic assessments of hands and feet (electronic format)

3RD MONTH VISIT

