 1. Physician completes VAS Physician global assessment of disease activity (joint and skin) 0-100;
 2. Patients completes pain VAS (0-100), global VAS (0-100), HAQ, PsAID12
- US assessment:
 1. US-score PsA-SIR
- X-ray assessment of hands and feet:
 1. Posterior-anterior radiographic assessments of hands and feet (electronic format)

CLINICAL ASSESSMENT

The demographic variables describing the patients will be age, sex, ethnic group, family history, body weight, height and smoking. On enrolment in the study, a detailed medical history will be recorded mostly focusing on PsA (onset of symptoms, date of diagnosis), related treatment (current and previous medication, reason for withdrawal) and associated comorbidities (e.g. SpA spectrum comorbidities). To assess comorbidities, disease specific recommendations will be followed.⁽¹⁷⁾

To increase feasibility and reliability metabolic syndrome will be defined as follows: 1) BMI > 30 kg/m²; 2) a diagnosis of type 2 diabetes mellitus and 3) a diagnosis of hypertension.⁽¹⁸⁾

Each patient considered eligible for the study will be classified according to clinical subset(s) of PsA:

- 1- Monoarticular or asymmetric oligoarthritis with or without dactylitis.
- 2- Symmetric polyarthritis similar to rheumatoid arthritis.
- 3- Classic psoriatic arthritis confined to distal interphalangeal joints of hands and feet.
- 4- Spondylitis with or without peripheral joint involvement
- 5- Arthritis mutilans

CLINICAL EFFICACY

Clinical response and clinical remission will be based on the following variables:

- 1- Minimal Disease Activity (MDA)
- 2- Disease Activity for Psoriatic Arthritis (DAPSA)
- 3- ACR response score

The sonographer should be blinded to minimize bias associated with disease activity score evaluation. In addition, every effort should be made to ensure that the same member of staff performs the disease activity assessment on successive visits for a given patient.

The MDA calculation will be based on the evaluation of 7 variables:

- a) 68 tender joints count (≤ 1)
- b) 66 swollen joint count (≤ 1)
- c) BSA ≤ 3
- d) Patient pain VAS (≤ 15 mm);
- e) Patient global disease activity VAS (≤ 20 mm);
- f) HAQ (≤ 0.5);
- g) Leeds Enthesitis Index (LEI) tender enthesal points (≤ 1)

Patients will be classified as having MDA if they meet 5 out of these 7 criteria (value in brackets).

The DAPSA calculation is based on the evaluation of 5 variables:

- a) 68 tender joints count
- b) 66 swollen joint count

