- c) Patient's pain (VAS)
- d) Patient's global disease activity assessment (VAS)
- e) C-reactive protein

As a result the DAPSA index gives a value with:

- >28 indicating high disease activity
- 14-28 indicating moderate disease activity
- 4-13 indicating low disease activity
- ≤ 4 indicating complete remission

Using DAPSA the clinical response can be defined:

- Minor : 50% DAPSA change from baseline
- Moderate: 75% DAPSA change from baseline
- Major : 85% DAPSA change from baseline

The ACR20 response criteria require $\geq 20\%$ [ACR50 $\geq 50\%$ or ACR70 $\geq 70\%$] improvement in both the TJC and SJC, as well as a 20% improvement in 3 of the following 5 items:

1. patient global assessments of disease activity (VAS),
2. patient reported pain score (VAS),
3. physician global assessment (VAS),
4. Health Assessment Questionnaire (HAQ),
5. either ESR or CRP.

METHODS OF ASSESSMENT

Patient's assessment will be performed according to the core set of domains for PsA proposed by the Group for Research and Assessment of Psoriasis and Psoriatic Arthritis (GRAPPA) and Outcome Measures in Rheumatology (OMERACT).^(19,20)

Assessment of **Peripheral Joint Activity** will be performed using the 68 tender joint count and the 66 swollen joint count. Positive joints will be recorded and the total number of tender and swollen joints will be calculated. As it may be difficult to distinguish proximal inter-phalangeal (PIP) from distal inter-phalangeal (DIP) joint inflammation in the toes, if either the PIP or DIP of the toe is involved it should be marked as a PIP.

Patient global assessment (PtGA) and **Physician global assessment (PGA)** will be assessed by Visual Analogues Scores (VAS) as it is a reliable tool related to joint and skin disease activity. **VAS PGA of disease activity (0-100)**

Physicians will take into account both the severity of joint and skin disease when making the assessment on the scale. The left end corresponds to “completely inactive” and the right end to “highly active”.

- **VAS PtGA of disease activity (0-100)**

The patients are instructed to rate their overall state of disease (joint and skin) on the scale. Recall period: past week. The left end corresponds to “completely inactive” and the right end to “highly active”. The patients will mark their own assessment on the scales in the case report forms by themselves by placing a single vertical line through the bar.

- **VAS PtGA of pain (0-100)**

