US IMAGING						
US-score PsA-SIR		X		X	X	X
CR IMAGING						
X ray (hands-feet)		X			X	X
ADVERSE EVENTS			X	X	X	X

STATISTICAL ANALYSIS PLAN

VARIABLES: OUTCOME MEASURES

PRIMARY:

- MDA at 6 months

SECONDARY

- MDA at 12 months, sustained MDA at 6 AND 12 months
- DAPSA <3.3 at 6 months, 12 months, 6 AND 12 months
- Δ mSvH 0-12 and 0-24 months
- Δ HAQ 0-12 and 0-24 months
- Δ PSAID 0-12 and 0-24 months
- US-score PsA-SIR damage subscore at 0-6-12 months

US PREDICTORS

- US-score PsA-SIR
- US-score PsA-SIR inflammation subscore
- US-score PsA-SIR damage subscore

CLINICAL PREDICTORS

Based on the relevant literature clinical variables to be considered in the model include:

- Demographic and environmental factors:
 - Age
 - Gender
 - Smoking
 - BMI
- Clinical factors:
 - subset of PsA
 - time from symptoms onset to diagnosis
 - disease duration
 - disease activity (DAPSA and BASDAI)
 - HAQ score
 - tender joints / pain
 - comorbidities (FM, MetS)
- Serological factors:
 - Acute phase reactants
- Therapy factors:
 - Treatment (NSAIDs, steroids, DMARDs)

DESCRIPTIVE ANALYSES

Descriptive data will be provided for all outcomes according to data type; number of patients (N), mean, standard deviation (for interval data), median 25% and 75% quartiles (for ordinal data). Frequency (absolute and relative) distributions will be provided for categorical data. Two-sided p-values will be presented throughout.

PRIMARY ENDPOINT ANALYSIS

Prediction of 6 months MDA will use multivariate adjusted logistic models. A baseline model will include all the clinical variables. US predictors will be added as covariates to the clinical variables, assuming an additive model. The derived β coefficients were used to calculate prognostic indices, thereby creating weighted prediction models.

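### The clinical reference model omits the baseline physician global VAS and other recorded examiner findings, so ultrasound could be credited with information the examiner already had

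*Combined protocol and SAP*

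**What the plan says.** The primary objective is "to evaluate the additional value of US-score (US-score PsA-SIR) over clinical examination in detecting patients achieving MDA at 6 months". Under PRIMARY ENDPOINT ANALYSIS, "A baseline model will include all the clinical variables", and then "US predictors will be added as covariates to the clinical variables, assuming an additive model". The comparison is judged by AUC, NRI, IDI and ROC curves.

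The clinical variables are listed under CLINICAL PREDICTORS, introduced by "Based on the relevant literature clinical variables to be considered in the model include". Disease activity appears there as "disease activity (DAPSA and BASDAI"). The physician global is not in the list.

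The BASELINE VISIT section has "Physician completes VAS Physician global assessment of disease activity (joint and skin) 0-100", and the STUDY VISIT/SCHEDULE table confirms it at baseline. METHODS OF ASSESSMENT explains what it measures: "Physicians will take into account both the severity of joint and skin disease when making the assessment on the scale". Its only named analytic use is as one of the five further items of the ACR response (CLINICAL EFFICACY).

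**The concern.** An added-value claim is only as good as its reference model. Anything the examiner recorded before the scan belongs on the clinical side of the comparison. If such a finding is left out, and it carries prognosis that the listed variables miss, a US score correlated with it will pick up part of that prognosis. The model with US then looks better even if US contributes nothing new. An error of this kind favours the hypothesis under test.

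The physician global is the clearest example because it is the only global rating made by the physician. The global and pain scores inside DAPSA are the patient's. It is not the only omission.

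**Working it through.** **Step 1. Which examiner records reach the reference model?** Sources: BASELINE VISIT, CLINICAL EFFICACY, METHODS OF ASSESSMENT, CLINICAL PREDICTORS.

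| Baseline record | In the reference model? |
|---|---|
| Tender joint count | Yes: in DAPSA, and again in the tender-joint/pain item |
| Swollen joint count | Yes: in DAPSA |
| Clinical subset | Yes: listed |
| Treatment chosen | Yes: listed |
| Entheseal assessment | No |
| Dactylitis count | No |
| BSA | No |
| Physician global VAS | No |

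"The DAPSA calculation is based on the evaluation of 5 variables": two joint counts, patient pain, patient global and CRP. BASDAI is six questions put to the patient. Neither contains a physician rating.

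MDA has seven components. Baseline values of five are in the reference model: both joint counts, patient pain and patient global through DAPSA, and HAQ directly. The two missing are BSA and the Leeds Enthesitis Index, both examiner findings. The US score covers 12 entheses.

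**Step 2. How large could the effect be?** From SAMPLE SIZE: n = 250 and MDA probability 0.4. Everything else here is assumed, because the documents give no prognostic strength for the physician global and no correlation with US. The model is

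logit P(MDA) = a − 0.8·X − ln(OR)·P, with US = r·P + √(1−r²)·e

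X is the listed clinical index, P the part of the physician global not explained by X, and e is noise. All are independent standard normal, and a is set to give 40% MDA. OR is the factor by which the odds of MDA fall per SD of P. US has no effect of its own. Rejection is |z| > 1.96 for US over 1,500 runs per setting. The AUC gain comes from one sample of 200,000.

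| OR per SD | r | Rejection, P omitted | AUC gain, P omitted |
|---|---|---|---|
| 1.0 | 0.2 / 0.4 / 0.6 | 5.5% / 5.3% / 5.0% | 0 / 0 / 0 |
| 1.25 | 0.2 / 0.4 / 0.6 | 5.2% / 9.4% / 14.9% | 0.0004 / 0.0013 / 0.0026 |
| 1.5 | 0.2 / 0.4 / 0.6 | 9.3% / 20.8% / 38.4% | 0.0011 / 0.0044 / 0.0088 |
| 2.0 | 0.2 / 0.4 / 0.6 | 14.7% / 45.9% / 78.7% | 0.0029 / 0.0111 / 0.0244 |

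With P in both models, rejection is 4.1-6.7% in every setting and the AUC gain is 0.

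Hand check at OR 1.5, r = 0.4. The borrowed US coefficient is about ln(1.5) × 0.4 = 0.405 × 0.4 = 0.162. Its SE is about 1/√(250 × 0.4 × 0.6) = 0.129, so z is about 1.26. Rejection is then about Φ(1.26 − 1.96) = 24%. The simulated 20.8% is a little lower, as expected, because the spread of X reduces the information.

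A second simulation used a likelihood-ratio test, OR 0.74 to 0.50 per SD (about 1.35 to 2.0 in the table's direction) and r 0.2 to 0.5. With P omitted, rejection was 7-66% and the in-sample AUC gain 0.004-0.024. With P included, they were 5-7% and about 0.003. The 0.003 is optimism from refitting, so the low end is an excess of only about 0.001.

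**Step 3. What does another term cost?** The plan says the sample supports 10 predictors by a rule of thumb. Assuming that rule is 10 events per predictor, 250 × 0.4 = 100 events and 100/10 = 10, which reproduces the plan's figure. An eleventh predictor gives 100/11 = 9.1. At 300 × 0.8 = 240 completers it is 96/11 = 8.7. Restoring 10 per predictor would need 275 evaluable patients, or 275/0.8 = 344 enrolled.

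The list already exceeds 10. Counting four terms for five subsets, two or three for treatment, and one or two each for tender joints/pain and acute phase reactants gives 19-22 parameters, or 100/22 = 4.5 to 100/19 = 5.3 events each. One more makes 20-23 (4.3-5.0). Three further terms in a sensitivity analysis make 23-26 (3.8-4.3).

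**The case against.** Several points on the other side are sound.

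- A reader might infer that the physician global is the only record of the clinician's examination, so that the examination is missing from the reference model. The documents do not support this. Joint counts enter through DAPSA, and subset and treatment are listed. Treatment is the rheumatologist's own decision, made before the scan, so it may carry some of the same judgement.
- Choosing predictors from the literature is legitimate, and nothing in the documents shows that the physician global predicts MDA. This stands as a reason to call the bias possible rather than shown.
- Singling out the physician global is partly arbitrary. Entheseal findings and BSA have at least as strong a claim, since both bear directly on MDA components. This stands, and it widens the point.
- The list is worded as open, so the physician global is not expressly excluded. This does not help the plan. Either the list is the model and the score is missing, or the reference model is not fixed in advance.
- The rejection rates concern a test of the US term, whereas the plan names AUC, NRI and IDI. This is fair: the AUC column is closer to the plan's criteria, and its gains are small in most settings. NRI and IDI were not simulated.

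**Conclusion.** The omission is confirmed by the documents. The physician global is recorded at baseline, is not listed, and does not enter through DAPSA or BASDAI. Entheseal assessment, dactylitis count and BSA are missing in the same way, and no reason is given.

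The consequence is conditional. It needs the omitted findings both to predict MDA beyond the listed variables and to correlate with US given those variables. A reader might conclude that US will be falsely credited, or take the upper rejection rates as the expected error. The documents support neither, since they give no value for either condition. Under the assumed values the excess runs from nil (about 5% rejection, no AUC gain, at OR 1.0) to substantial (79% and 0.024 at OR 2.0, r = 0.6).

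The change is worth making before the primary analysis because the data are already collected and a positive result would otherwise be open to this challenge.

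**What to change.** 1. Add the baseline physician global VAS (linear, 0-100) to CLINICAL PREDICTORS and include it in both the clinical and the clinical-plus-US model.
2. Keep the separate tender-joint/pain item. Replacing it might look cost-free because its contents are inside DAPSA. But DAPSA fixes their relative weights, and dropping the separate term could reopen the same kind of omission.
3. Pre-specify a sensitivity analysis that also adds entheseal count, dactylitis count and BSA to both models.
4. Require that the physician global be scored before the US result is known. This must be a new requirement. ULTRASONOGRAPHIC ASSESSMENT places the scan after the treatment decision, not after this form, and CLINICAL EFFICACY states blinding for the sonographer only.

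The cost is one more coefficient in the main model (about 9.1 instead of 10 MDA events per predictor at N = 250 on the plan's count of 10, a count the list already exceeds), three more in the sensitivity analysis, and one procedural sentence. No new data are needed.

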- results in persistent or significant disability/incapacity
- constitutes a congenital anomaly/birth defect
- requires inpatient hospitalization or prolongation of existing hospitalization.

ULTRASONOGRAPHIC ASSESSMENT

Sonographic evaluations will be performed by expert ultrasonographers on the same day of clinical assessment and must invariably be performed after the clinical decision to change the patient's treatment. Furthermore, results of ultrasonographic evaluation should not be taken into account for the choice of treatment.

Grey scale (GS) and power Doppler (PD) sonography will be performed in 44 joints, 36 tendons, 12 entheses and 2 bursae (US-score-PsA-SIR) using a high standard US machine and multi-frequency linear transducers (high frequency probe at least 14 Mhz).

In the absence of a definition of the ultrasound **bone proliferation** in PsA, we propose to use the OMERACT definition of osteophyte (formation of excess bone at the joint margins).^(21, 22) Score dichotomous: 0 – Absent, 1 – Present.

In accordance with Terslev L. et al⁽²³⁾ the elementary lesions considered to evaluate **enthesitis** were: hypoechogenicity (indicate increased thickness with blurring of the tendon margins); increased thickness of tendon insertion; enthesophyte (the step up of the bony prominence at the end of the normal bone contour is marked with white arrowheads); calcifications; bone erosion at the enthesis; Doppler at enthesis <2 mm from the bone insertion. In addition to single elementary lesions, global definition of enthesitis will be recorded.

Erosions will be defined as an intra-articular discontinuity of the bone surface that is visible in 2 perpendicular planes.⁽²⁴⁾

Sonographically the two criteria for the definition of **bursitis** have been represented by: pathological effusion into the bursae (shown as an anechoic material) and hypertrophy of the synovial membrane (displayed as material into the bursae, which can appear hypoechoic, isoechoic or hyperechoic compared with subcutaneous fat). Bursitis may also be characterized by the presence of the Doppler signal within the synovial proliferation. For some bursae as the bag deep infrapatellar bursa and deep Achilles bursa minimum fluid distension, in the absence of synovial proliferation, are considered physiological.

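### The protocol blinds the sonographer but does not keep the baseline US result from the examiner who records four of the seven month-6 MDA items, so the estimated added value of US can be biased

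*Combined protocol and SAP*

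**What the plan says.** The primary outcome in the SAP is "MDA at 6 months". Under Clinical efficacy, "Patients will be classified as having MDA if they meet 5 out of these 7 criteria". The seven items are tender joints, swollen joints, BSA, patient pain VAS, patient global VAS, HAQ and LEI.

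The same section contains the only blinding rule that operates between clinical examination and US: "The sonographer should be blinded to minimize bias associated with disease activity score evaluation". It does not spell out what the sonographer is blinded to, but the stated purpose concerns disease activity scoring. It continues that "every effort should be made to ensure that the same member of staff performs the disease activity assessment on successive visits" for a given patient.

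Ultrasonographic assessment adds three rules:
- "Sonographic evaluations will be performed by expert ultrasonographers on the same day of clinical assessment"
- the scan "must invariably be performed after the clinical decision" to change treatment
- "results of ultrasonographic evaluation should not be taken into account for the choice of treatment"

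Elsewhere, the central X-ray readers are blinded to clinical data and film order (Radiographic assessment). The data system has password protection and range checks (Ethics), with no stated limit on who sees US data.

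**The concern.** Blinding the sonographer keeps clinical findings out of the US score. The study also needs the reverse protection, because US is the predictor on trial and the examiner produces much of the outcome. An examiner who remembers an active or a quiet baseline scan may judge a borderline joint or enthesis differently at month 6. The cut-off for tender joints, swollen joints and LEI is one or fewer, so a single call can change an item. Outcome error that depends on the predictor does not average out as random error does, and it enters the AUC, NRI and IDI comparisons that carry the primary claim.

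The request for the same assessor over time is sensible for consistency. Combined with same-day scanning, it makes it more likely that the month-6 examiner was present when the baseline scan was done.

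**Working it through.** **Who records each MDA item** (Clinical efficacy; 6th month visit; Methods of assessment)

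| Source | Items | Count |
|---|---|---|
| Examiner | tender joints, swollen joints, BSA, LEI | 4 |
| Patient | pain VAS, global VAS, HAQ | 3 |

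MDA needs 5 items, so the fewest examiner items in any MDA is 5 − 3 = 2. The patient items alone can never give MDA. One altered item changes MDA status only in a patient who meets exactly 4 or exactly 5 criteria.

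**What each safeguard covers**

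| Rule | Baseline clinical data | Month-6 items v month-6 scan | Month-6 items v baseline US |
|---|---|---|---|
| Sonographer blinded | protects the US score, not these | the same | no |
| Scan after decision to change treatment | yes | probably, if treatment changes; not stated if it does not | no |
| US not used to choose treatment | limits use, not knowledge | limits use, not knowledge | limits use, not knowledge |

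The last column matters most. The SAP does not name the time point of the US predictor, but predicting a month-6 outcome implies baseline. No rule keeps that result from the month-6 examiner.

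**Illustration of size.** The plan gives no figure to reproduce here. One input is from the documents: MDA probability 0.40 (Sample size). The rest are assumptions: US has no predictive value, it is split at its median, and a share *f* of patients in each half has the MDA label moved, downward in one half and upward in the other. The result is unadjusted.

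OR = [(0.4 + f)/(0.6 − f)] / [(0.4 − f)/(0.6 + f)]

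AUC = 0.5 + ½ × [(0.4 + f)/(2 × 0.4) − (0.6 − f)/(2 × 0.6)]

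- f = 0.025: OR = (0.425/0.575)/(0.375/0.625) = 0.739/0.600 = 1.23; AUC = 0.5 + ½ × (0.531 − 0.479) = 0.53.
- f = 0.05: OR = (0.45/0.55)/(0.35/0.65) = 0.818/0.538 = 1.52; AUC = 0.5 + ½ × (0.5625 − 0.4583) = 0.55.

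Misclassification required:
- f = 0.025: 0.025/0.40 = 6.3% of true MDA patients in one half and 0.025/0.60 = 4.2% of non-MDA patients in the other.
- f = 0.05: 0.05/0.40 = 12.5% and 0.05/0.60 = 8.3%.

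If labels move in one half only, with the other left at 40%:
- 2.5% moved down: OR = (0.40/0.60)/(0.375/0.625) = 1.11.
- 5% moved down: OR = (0.40/0.60)/(0.35/0.65) = 1.24; overall MDA is 0.375, so AUC = 0.5 + ½ × [0.40/(2 × 0.375) − 0.60/(2 × 0.625)] = 0.5 + ½ × (0.533 − 0.480) = 0.53.

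**The case against.** The best case against the point is that the gap is only silence. No text says the examiner receives the baseline scan, and about six months separate that scan from the outcome. The scan follows the decision to change treatment, may not guide treatment choice, and comes after the clinical items in the visit lists. Three of the seven items are the patient's, and BSA is skin area, which the scan does not measure. Withholding a scan report for six months in a usual-care observational study is also a real restriction.

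Much of this stands. The month-6 scan is a secondary matter, since it is not the implied predictor, although a visit list is not an ordering rule. Tender joints and LEI also depend on the patient's response. Patients are not said to be unaware of their scan, so their own items are not fully immune either. The shift rates above have no source in the documents.

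Three stronger readings are tempting and should be resisted:
- **That the bias inflates the value of US.** The documents state no expected direction between baseline US and MDA. Examiners with opposite expectations would partly cancel, and a shift against a true association would weaken it.
- **That nobody but the sonographer is blinded.** The X-ray readers are, although X-ray plays no part in MDA.
- **That sonographer and clinician are already separate people.** The authorship table under Publication rules lists them in separate columns, and blinding the sonographer suggests it, but no text requires it.

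What the objection does not supply is any rule that conceals baseline US from the outcome examiner. The cost of concealment is limited because the protocol already excludes US from treatment choice, although it does not exclude every other use.

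**Conclusion.** The point holds as an unprotected route for bias in the primary outcome. A reader might infer that examiners will see the US result, or that the study's result will be too favourable to US; the documents support neither. They support this much: at least two examiner-recorded items underlie every MDA, the same examiner is sought across visits, and nothing conceals the baseline US result from that person. Knowledge of US can therefore bias the estimated added value, in a direction and by an amount that cannot be derived from the text.

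If labels moved systematically with US at the assumed rates, a worthless marker would show an odds ratio of about 1.1 to 1.5. The upper end needs misclassification in both directions. These figures rest on a 40% MDA rate, a median split and no adjustment for the clinical model, so they do not estimate the bias in the planned increment. The change should be made because it protects the primary outcome at little cost.

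**What to change.** 1. At every visit with a scan, the clinical assessor completes and locks the joint counts, BSA and LEI before the scan, whether or not treatment changes.
2. US scores and reports stay out of that assessor's view, in the data system and in local reports, until the month-6 MDA items are entered. Any unblinding is recorded with its date.
3. Patients for whom one person held both roles, or whose assessor was unblinded, are flagged, and the primary analysis is repeated without them.

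**Cost.** A visit-order rule, a data-access restriction, later sight of a research scan that the protocol already bars from treatment choice, and a smaller sample in the sensitivity analysis. No extra assessor is needed and the planned sample size does not change. The change does not address what patients themselves know of their scan.
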